3.7 Variables/ Parameters

3.7.1 Dependent Variables

3.7.1.1 Primary Outcome

The primary outcome investigated is the central line-associated bloodstream infection (CLABSI) rate, expressed in cases per 1000 catheter days. The diagnosis of CLABSI will be based on the CDC-NHSN definition.

3.7.1.2 Secondary Outcomes

The secondary outcomes investigated included:

- i. ICU Length of stay of patients diagnosed with CLABSI
- ii. Healthcare costs of patients diagnosed with CLABSI
- iii. Antimicrobial resistance profiles of the bacterial species isolated from patients diagnosed with CLABSI

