1. INTRODUCTION

Central venous catheters (CVCs) are indispensable in modern critical care as they are highly reliable as intravenous access for administration of vasopressors, inotropes, irritant solutions, total parenteral nutrition and for haemodynamic monitoring. The average central line utilisation ratios in the ICUs across 45 countries were reported at 0.525 (Rosenthal et al., 2021). CVC usage is associated with complications, including central line-associated bloodstream infections (CLABSIs).

The rate of CLABSI is reported at 4.45 per 1000 central line days in ICUs across 45 countries from 2013 – 2018 (Rosenthal et al., 2021). This in turn, is translated to increased healthcare costs and mortality. One of the strategies to reduce the incidence of CLABSI is the use of antimicrobial-impregnated CVCs. These antimicrobial-impregnated CVCs, which can be coated with either antibiotics (e.g. rifampin, minocycline, etc.) or antiseptics (e.g. chlorohexidine, silver sulphadiazine, benzalkonium chloride, etc.) or both, are proposed to be able to reduce the incidence of CLABSI by inhibiting microorganism colonisation on CVCs. A meta-analysis published in 2018 concluded that antimicrobial-impregnated CVCs were significantly effective in reducing CLABSIs and catheter colonisations (Wang et al., 2018). Nevertheless, its efficacy and beneficial effects, particularly in terms of patients' outcome had not been homogeneously demonstrated across literature. Moreover, antimicrobial-impregnated CVCs are more expensive compared to non-impregnated ones, and hence its cost-effectiveness remains doubtful.

To date, in our local setting, no study evaluates the efficacy and economic impact of antimicrobial-impregnated CVCs and on patients' outcome. Cost-effectiveness evaluation is important to provide value-based care in clinical practice. This study aims to evaluate the clinical and economic treatment of antimicrobial-impregnated CVCs vs Non-impregnated CVCs in prevention of CLABSI.

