1.1 Research Questions

1. Is there any difference in central line-associated bloodstream infection (CLABSI) rates between patients using antimicrobial-impregnated central venous catheters (CVCs) and non-impregnated CVCs in Malaysia adult Intensive Care Unit (ICU)?

2. Does the use of antimicrobial-impregnated central venous catheters (CVCs) in central line-associated bloodstream infection (CLABSI) prevention in Malaysia adult Intensive Care Unit (ICU) affect patient length of stay when compared to non-impregnated CVCs?
3. Does the use of antimicrobial-impregnated central venous catheters (CVCs) in central line-associated bloodstream infection (CLABSI) prevention in the adult Intensive Care Unit (ICU) setting affect healthcare costs when compared to non-impregnated CVCs?
4. How antimicrobial resistance features of the bacteria causing central line-associated bloodstream infection (CLABSI) may differ in patients using antimicrobial-impregnated central venous catheters (CVCs) compared to non-impregnated CVCs?

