2. OBJECTIVES

Primary objective:

- To compare the incidence of central line-associated bloodstream infection (CLABSI) rate in patients using antimicrobial-impregnated central venous catheter (CVCs) and non-impregnated CVCs in Malaysia adult Intensive Care Unit (ICU)

Secondary objectives:

- To determine the length of stay of patients using antimicrobial-impregnated central venous catheter (CVCs) vs non-impregnated CVCs in Malaysia adult Intensive Care Unit (ICU)
- To undertake a cost-effectiveness analysis in prevention of central line-associated bloodstream infection (CLABSI) between patients using antimicrobial-impregnated central venous catheters (CVCs) and non-impregnated CVCs in Malaysia adult Intensive Care Unit (ICU)
- To compare the antimicrobial resistance features of the bacterial species that caused central line-associated bloodstream infection (CLABSI) between patients using antimicrobial-impregnated central venous catheter (CVCs) and that of non-impregnated CVCs in Malaysia adult Intensive Care Unit (ICU)

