3.7.2 Other Parameters

Baseline patient data will be included as concomitant study parameters. Relevant patient and clinical data including basic demographic information (age, gender, and ethnicity), known underlying diseases, previous antibiotic exposure within 90 days, and admission date will be extracted from the clinical database for correlation and risk factor analyses.

For patients diagnosed with CLABSI, information including the number of days a patient spent in the hospital prior to strain isolation, number of days and type(s) of antibiotics used in said patient, hospital-generated antibiograms for each strain, patient risk factors for nosocomial infection associated with an isolate, previous surgeries or hospitalizations of the patient prior to isolation, location of a patient within the hospital prior to strain isolation and ICU admission, and any other information pertinent to a specific strain that will not identify a patient will be collected.

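### ICU stay and cost are to be compared between catheters but are defined only in CLABSI patients, with no discharge status listed and no rule for stays that end in death

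*Combined protocol and SAP*

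**What the plan says.** The purpose is a comparison by catheter type. Research question 2 (section 1.1) asks whether impregnated catheters "affect patient length of stay when compared to non-impregnated CVCs", and question 3 asks the same of healthcare costs. Section 2 sets the matching objectives: "To determine the length of stay of patients using antimicrobial-impregnated central venous catheter (CVCs) vs non-impregnated CVCs", and for cost, "To undertake a cost-effectiveness analysis in prevention of central line-associated bloodstream infection (CLABSI) between patients using antimicrobial-impregnated central venous catheters".

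Section 3.7.1.2 defines the outcomes more narrowly, as "ICU Length of stay of patients diagnosed with CLABSI" and "Healthcare costs of patients diagnosed with CLABSI".

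For all patients, section 3.7.2 lists demographics and then "known underlying diseases, previous antibiotic exposure within 90 days, and admission date will be extracted from the clinical database". For CLABSI patients it adds antibiotic, strain and prior-stay data, ending with "any other information pertinent to a specific strain that will not identify a patient will be collected". Section 3.8.1 builds the collection form from the study parameters. Section 3.9 names chi-square, Fisher's exact test and logistic regression for CLABSI risk factors. It gives no method for stay or cost.

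Apart from reference titles, mortality appears once, in the Introduction, on the consequence of CLABSI: "This in turn, is translated to increased healthcare costs and mortality".

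**The concern.** Two gaps act together.

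First, the patients in whom stay and cost are measured are not the patients the objectives describe. Whether a patient develops CLABSI is decided after randomisation and is the very thing the catheter is meant to change. Comparing arms within that group gives up the protection of randomisation. It also leaves out bed-days saved by an infection that was prevented, because a patient who avoids CLABSI is no longer in the group.

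Second, a stay can end in discharge or in death, and the plan does not separate the two. Where patients who die spend less time in the ICU than survivors, more deaths give a shorter mean stay and, if cost rises with days, a lower mean cost. The Potential Research Impact section treats shorter stay and lower cost as the expected benefit, so a result of that kind would naturally be read as favourable. With no deaths reported beside it, the reader could not see the alternative explanation. The answers to research questions 2 and 3 are what is at stake.

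**Working it through.** **1. Population, side by side.** Sections 1.1 and 2: patients by catheter type. Section 3.7.1.2: patients diagnosed with CLABSI. Both cannot be the analysis population of one comparison.

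**2. Where death could enter the plan.**
- Outcomes (3.7.1.1, 3.7.1.2): CLABSI rate, stay, cost and resistance profiles. No death.
- Parameters (3.7.2): an admission date, but no ICU discharge date, discharge status or vital status. The closing catch-all covers strain information only.
- Form (3.8.1): study parameters only.
- Analysis (3.9): no method for stay or cost, so no rule for a stay that ends in death.
- Exclusions (3.4): a catheter in place for under 48 hours removes some early deaths, but not later ones.

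**3. Size of the effect.** The plan has no stay, cost or mortality figure to reproduce, so the inputs here are assumptions. Let L be survivors' mean stay (the same in both arms), t the mean stay of those who die, and m the ICU mortality.

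Mean stay = (1 − m) × L + m × t, so the difference between arms = (difference in m) × (L − t).

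With L = 12 and t = 5:
- m = 20%: 0.80 × 12 + 0.20 × 5 = 10.6 days
- m = 25%: 0.75 × 12 + 0.25 × 5 = 10.25 days
- m = 30%: 0.70 × 12 + 0.30 × 5 = 9.9 days

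A gap of 5 points moves the comparison by 10.6 − 10.25 = 0.35 day, and one of 10 points by 10.6 − 9.9 = 0.7 day, with no catheter effect on survivors' stay. For L from 10 to 20 and t from 4 to 7, L − t runs from 3 to 16 days, so a 10-point gap gives 0.3 to 1.6 days. The arm with more deaths looks shorter whenever t < L.

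**4. How large a gap could the protocol's own mechanism produce?** The route named in the Introduction is from CLABSI to death. Section 3.6 gives 12.18 CLABSI per 1000 catheter days, a 30% reduction and 55 patients per arm. Catheter days per patient are assumed.

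| Catheter days each | Expected CLABSI, control | Expected CLABSI, impregnated (× 0.7) | Avoided | Avoided / 55 |
|---|---|---|---|---|
| 5 | 55 × 5 × 0.01218 = 3.35 | 2.34 | 1.0 | 1.8% |
| 10 | 6.70 | 4.69 | 2.0 | 3.7% |
| 20 | 13.40 | 9.38 | 4.0 | 7.3% |

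Even if every avoided CLABSI were an avoided death, which is a ceiling, the mortality gap would be 1.8 to 7.3 points. With L − t = 7 days, that is 0.13, 0.26 or 0.51 day. By this route the extra deaths fall in the non-impregnated arm, so the distortion would hide part of a benefit of the impregnated catheter.

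**5. Size of the group in section 3.7.1.2.** The same table gives about 3 to 13 CLABSI patients in the control arm and 2 to 9 in the other. The step 3 illustration describes whole arms. The mechanism is the same in the CLABSI-only group, but a comparison of so few patients would carry little information.

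**The case against.** The strongest reply has four parts.

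- **Silence is not refusal.** The list in 3.7.2 also omits the ICU discharge date, which the stay outcome needs, and catheter dates, which the primary outcome needs. It is plainly not exhaustive, and its source is a clinical database that probably holds deaths. This stands. A reader might infer that death will go unrecorded or that the data could not be recovered. The document supports neither. It shows only that the plan does not list death or say how it will be used.
- **The distortion is conditional.** It needs mortality to differ between arms, and no figure in the document says that it will. This stands too. A reader might infer that the trial will report a false saving for the impregnated catheter. By the protocol's own mechanism (step 4) the distortion runs the other way and is smaller than the 10-point illustration.
- **Chance imbalance is not bias.** With equal true mortality, an uneven split of deaths is sampling variation, already carried in the standard error of mean stay. At 25% mortality, 50 per arm and a 7-day difference, the mix of deaths alone contributes √(2 × 49 × 0.1875 / 50) = 0.61 day to that standard error, where 0.1875 = 0.25 × 0.75. A chance gap in deaths therefore should not be presented as bias.
- **Raw stay and cost are legitimate.** Resources really do stop being used at death, and ICU-free days or a competing-event analysis answers a different question from bed use. This is why raw stay and cost should remain.

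None of this resolves the mismatch between sections 2 and 3.7.1.2, or supplies a rule for death before the data are seen.

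**Conclusion.** The point holds as a gap in specification. Stay and cost are meant to be compared by catheter, yet they are defined in a group selected after randomisation, with no discharge date, discharge status or handling of death set out. On assumed values of 12 days for survivors and 5 for deaths, a 5- to 10-point mortality gap moves the difference in mean stay by 0.35 to 0.7 day, in either direction. Cost moves the same way if it rises with days. The size rests wholly on assumed stay and mortality figures; the direction rests on deaths coming earlier than survivors' discharge.

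It does not follow that research questions 2 and 3 will be answered wrongly, because no mortality difference is documented. What follows is that a reader of the planned results could not separate shorter stays from earlier deaths. The CLABSI rate analysis is unaffected by this point.

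**What to change.** - **3.7.2:** add ICU discharge date and status at ICU discharge (alive or dead) for all randomised patients.
- **3.7.1.2 and 3.9:** state that stay and cost are compared by randomised arm in all randomised patients, so that 3.7.1.2 agrees with section 2, and name the method. Say how this population relates to the exclusions in 3.4 that can only be known after the catheter is in place. Stay and cost in CLABSI patients can be kept as description.
- **Reporting:** show ICU deaths by arm beside the stay and cost results.
- **Supporting analysis:** add time to alive ICU discharge with death as a competing event. Keep raw stay and cost as the measures of resource use.

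The cost is two fields, which the existing ICU record can be expected to hold, a few lines in 3.9 and one extra analysis. The sample size and the primary analysis need no change for this point.

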3.9 Data Analysis

The data will be analysed using the SPSS Software. Descriptive statistics will be expressed as percentages unless otherwise stated. Categorical variables will be expressed as percentages and compared using the Chi-square or Fisher's exact test, whichever is appropriate. Variables with a univariate test value of less than 0.05 (p-value) will be included in a multivariate analysis using a logistic regression model. Odds ratios (OR) and 95% confidence intervals (CI) will be calculated to identify the risk factors associated with the development of CLABSI in patients. In all instances, a p-value of less than or equal to 0.05 will be considered significant.

FUNDING

This study will be funded by Teleflex Research Grant (RM50000).

RESEARCH DATA MANAGEMENT

All data collected will be handled confidentially according to the Good Clinical Practice Guidelines. The paper case report forms will be stored within a locked cabinet at the Department of Anaesthesiology, Faculty of Medicine, Universiti Malaya. The electronic case report forms will be kept in a password-protected laptop. Only the study investigators will have access to the research data. The data will be kept for seven years upon completion of study. The results of the study will be reported in a thesis. The results will also be presented in conferences and published in scientific journals.

POTENTIAL RESEARCH IMPACT

The usage of antimicrobial-impregnated central venous catheters (CVCs) among adult critically ill patient in the Intensive Care Unit (ICU) can reduce central line-associated bloodstream infections (CLABSIs) and this will translate to reduced patients' length of stay and healthcare costs.

GANTT CHART

	2023												2024											
Research Activities	3	4	5	6	7	8	9	10	11	12	1	2	3	4	5	6	7	8	9	10	11	12		
Ethics submission	█	█																						
Patient recruitment			█	█	█	█	█	█	█	█	█	█	█	█										
Data collection			█	█	█	█	█	█	█	█	█	█	█	█										
Data analysis															█	█	█							
Completion and submission of manuscript																		█	█	█				
Publication and scientific presentations																					█	█		

REFERENCES

- Alotaibi, N. H., Barri, A., & Elahi, M. A. (2020). Length of Stay in Patients With Central Line-Associated Bloodstream Infection at a Tertiary Hospital in the Kingdom of Saudi Arabia. *Cureus, 12*(10). <https://doi.org/10.7759/CUREUS.10820>

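### ICU stay and healthcare cost are defined only in patients who develop CLABSI, while the research questions and objectives ask about all patients by catheter type

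*Combined protocol and SAP*

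**What the plan says.** Section 3.7.1.2 lists the first two secondary outcomes as "ICU Length of stay of patients diagnosed with CLABSI" and "Healthcare costs of patients diagnosed with CLABSI".

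The questions these outcomes should answer are wider. In section 1.1, question 2 asks whether using impregnated catheters would "affect patient length of stay when compared to non-impregnated CVCs", and question 3 whether it would "affect healthcare costs when compared to non-impregnated CVCs". Section 2 sets two matching objectives: "To determine the length of stay of patients using antimicrobial-impregnated central venous catheter (CVCs) vs non-impregnated CVCs", and "To undertake a cost-effectiveness analysis in prevention of central line-associated bloodstream infection (CLABSI) between patients using" one catheter type or the other. None of these is limited to infected patients.

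Other parts of the plan bear on the point:

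- **Section 3.7.2** lists data for all patients, ending with "previous antibiotic exposure within 90 days, and admission date will be extracted from the clinical database for correlation and risk factor analyses". It names no ICU discharge or death date and no cost. Its second paragraph adds items for CLABSI patients only.
- **Section 3.9** says "Categorical variables will be expressed as percentages and compared using the Chi-square" or Fisher's exact test, followed by logistic regression for CLABSI risk factors. It gives no comparison of stay or cost and no cost-effectiveness method.
- **Potential Research Impact** (after section 3.9) expects fewer infections to lead to shorter stay and lower cost.
- **The Introduction** gives the higher price of impregnated catheters as the reason their cost-effectiveness is in doubt. No section says whether healthcare costs include the catheter.

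**The concern.** The outcome definitions and the objectives describe different populations, and nothing elsewhere reconciles them. Three consequences follow if the outcomes are used as written to compare arms.

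1. **The comparison is not randomised.** Infection status is determined after randomisation and is what the catheter is meant to change. The infected patients in the two arms need not be alike.
2. **The expected benefit is excluded.** The plan expects gains through infections that do not happen. A patient whose infection was prevented is not a CLABSI patient and so drops out of outcomes i and ii.
3. **The cost-effectiveness analysis lacks its inputs.** Incremental cost per CLABSI avoided needs mean cost per arm over all patients. The extra catheter price is also paid for every uninfected patient, and outcome ii omits all of them.

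At stake are two of the three secondary objectives. Outcome iii (resistance profiles) is properly limited to CLABSI isolates and agrees with question 4.

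**Working it through.** The plan gives no figure for stay or cost, so there is none to reproduce. The mismatch is shown by the text, and the arithmetic shows its size.

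**Inputs from section 3.6.** Control rate 12.18 per 1000 catheter-days; 30% reduction, read as relative, so 12.18 × 0.7 = 8.526 per 1000; 50 patients per arm evaluable, 55 recruited.

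**Assumptions.** Catheter-days per patient are not given. I use 5, 10 and 14, the same for every patient, with one catheter each.

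**Patients contributing to outcomes i and ii.** P(CLABSI) = 1 − exp(−rate × days), with p0 for control and p1 for impregnated. Expected contributors are n × p0 and n × p1.

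| Catheter-days | p0 | p1 | 55 per arm | Share of 110 not contributing | 50 per arm |
|---|---|---|---|---|---|
| 5 | 0.0591 | 0.0417 | 3.2 v 2.3 | 95% | 3.0 v 2.1 |
| 10 | 0.1147 | 0.0817 | 6.3 v 4.5 | 90% | 5.7 v 4.1 |
| 14 | 0.1568 | 0.1125 | 8.6 v 6.2 | 87% | 7.8 v 5.6 |

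A cruder count, n × days × rate, gives similar numbers with 55 per arm: 3.3 v 2.3, 6.7 v 4.7 and 9.4 v 6.6.

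**Chance that at least one arm has fewer than 2 CLABSI patients.** With Bi the binomial probability of 0 or 1 cases in arm i, this is 1 − (1 − B0)(1 − B1). With 55 per arm it is 43%, 6% and 1% at 5, 10 and 14 days. With 50 per arm it is 50%, 9% and 2%.

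**What the restricted comparison can show.** Let L be mean stay without CLABSI and e the extra days from a CLABSI, both equal across arms.

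- All patients: (L + p1·e) − (L + p0·e) = −(p0 − p1)·e.
- CLABSI patients only: (L + e) − (L + e) = 0, whatever p0 and p1 are.

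For cost, let g be the catheter price gap and C the extra cost of a CLABSI (neither is given).

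- All patients: g − (p0 − p1)·C.
- CLABSI patients only: g if the catheter is costed, 0 if it is not.

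The value of p0 − p1 is 0.0173, 0.0329 and 0.0443, or about 1.7, 3.3 and 4.4 infections avoided per 100 impregnated-catheter patients. Impregnated catheters therefore save money whenever g is below about 1.7%, 3.3% or 4.4% of C. Under these conditions the CLABSI-only comparison cannot show that saving in expectation.

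**Precision if all patients are used.** If a CLABSI adds 5 to 15 ICU days (assumed), the expected stay difference runs from 0.0173 × 5 = 0.09 days to 0.0443 × 15 = 0.66 days. The 95% CI half-width with 55 per arm is t(0.975, 108) × √(2/55) = 1.982 × 0.191 = 0.378 SD of ICU stay. It is below 0.66 days only if that SD (not given) is below 0.66/0.378, about 1.8 days.

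**The case against.** **No between-arm comparison of infected patients is stated.** Section 3.7.1.2 names measures and a population, and section 3.9 gives no stay or cost analysis. This is true. But the questions and objectives call for a comparison by catheter type, and these are the only stay and cost outcomes available for it. Following the plan leads to that comparison.

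**Silence in section 3.7.2 proves little.** It covers parameters other than the outcomes, its list is open, and it also omits catheter-days, which the primary outcome needs. Section 3.8.1 promises a form covering every study parameter. This stands in part: an intention to collect stay and cost for everyone cannot be excluded. But section 3.8.1 adds no parameter or population, and the written outcome definitions remain restricted.

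**A model-based analysis could use CLABSI-patient costs.** The formula above needs only risk by arm, the price gap and a cost per CLABSI. But that cost is an excess over uninfected patients, so their costs are needed too.

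**Section 3.4 excludes some patients on facts known only after placement** (dwell under 48 hours, poor bundle compliance, more than one catheter). This is a separate problem and does not make an all-randomised population unsound. It does mean that the plan must say these patients are kept for stay and cost. Where they need further catheters, one catheter per patient no longer holds in the cost formula.

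**The counts depend on assumed durations.** This stands. At 20 and 30 catheter-days, contributors rise to 11.9 v 8.6 and 16.8 v 12.4 with 55 per arm, and the chance of fewer than 2 in an arm falls to about 0.1% or less. The 43% to 50% figures apply only at 5 days. The zero expected difference in stay does not depend on duration.

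**The all-patient estimate will be imprecise.** This also stands and limits what can be claimed. It does not justify answering a different question.

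**Conclusion.** The concern holds. As written, outcomes i and ii cannot answer research questions 2 and 3 or the stay and cost-effectiveness objectives. They would give a non-randomised comparison that leaves out the plan's own route to benefit.

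That the populations differ rests on the text alone. The zero expected difference rests on equal CLABSI effects in both arms and otherwise similar infected patients; if either fails, the difference may be non-zero but still would not measure the effect of catheter type. The counts rest on the plan's rates and the assumed catheter-days. This should be fixed; the primary outcome is unaffected.

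**What to change.** - Redefine outcomes i and ii as ICU length of stay and healthcare cost in all randomised patients, compared by assigned arm as a difference in means with a 95% CI. Add this analysis to section 3.9.
- Count stay to ICU discharge or death, and report ICU deaths by arm.
- State the cost components, including catheter price, and the cost source.
- Compute incremental cost per CLABSI avoided with costs and CLABSIs both counted in that same population.
- Add ICU discharge or death date and cost to the all-patient data in section 3.7.2.
- Keep CLABSI-only stay and cost as descriptive results.

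The cost is protocol wording plus these data for about 95 to 105 more patients (110 less the 14.8 to 5.5 expected CLABSI patients at 14 to 5 catheter-days). No new procedures are needed, but no cost source is named, so the extraction effort is unknown. Because the estimates will be imprecise, they should be presented with their CIs and not as tests expected to reach significance.

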3.6 Sample Size

Our local data at ICU, UMMC reported the incidence of CLABSI per 1000 catheter days in the first 6 months of 2022, to be 12.18. Using SAS® for sample size calculation, in order to detect a clinically significant reduction of CLABSI by 30%, and assuming a two-sided type I error protection of 0.05 and a power of 0.80, we calculated a sample size of 50 patients is required. To incorporate a 10% drop out rate, we therefore aim to recruit 55 patients in each arm (antimicrobial-impregnated CVCs, n=55; non-impregnated CVCs, n=55). This will make up to a total sample size of 110.

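### The between-arm resistance comparison is confined to patients who develop CLABSI, so randomisation does not protect it, and it will rest on few isolates

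*Combined protocol and SAP*

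**What the plan says.** Section 1.1 (question 4) asks how resistance in the causative bacteria may differ by catheter type. Section 2 makes this a between-arm objective: "To compare the antimicrobial resistance features of the bacterial species that caused central line-associated bloodstream infection (CLABSI"), impregnated against non-impregnated.

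Section 3.7.1.2(iii) defines the outcome as "Antimicrobial resistance profiles of the bacterial species isolated from patients diagnosed with CLABSI". Section 3.8.2 takes isolates only from patients who develop CLABSI.

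Section 3.9 names no test for resistance. Its general rule compares categorical variables by chi-square or Fisher's exact test, and "In all instances, a p-value of less than or equal to 0.05 will be considered significant".

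No section defines a resistance outcome per randomised patient or per catheter-day, states power for it, or calls it descriptive only.

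**The concern.** Having a CLABSI is an event after randomisation, and it is the event the catheter is intended to prevent. Restricting the comparison to infected patients selects on something treatment may change, so the two infected groups can differ for reasons other than an effect on resistance. A higher resistant share in the impregnated arm could mean more resistant infections or only fewer susceptible ones. The share alone cannot separate the two.

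The number of isolates will also be small. If the general testing rule is applied, a p-value above 0.05 could be mistaken for evidence that the catheter does not affect resistance.

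**Working it through.** **Inputs from section 3.6.** The unit "reported the incidence of CLABSI per 1000 catheter days in the first 6 months of 2022, to be 12.18"; a 30% reduction, read as relative, gives 12.18 × 0.7 = 8.526 per 1000 catheter-days. Recruitment: "To incorporate a 10% drop out rate, we therefore aim to recruit 55 patients in each arm".

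**Assumptions not in the documents.** Mean catheter time of 5 to 14 days per patient, the resistant shares, one isolate per CLABSI, and all 55 per arm followed. Exclusions would lower the counts.

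**The plan's own figure.** No sample size is given for resistance. The only stated figure is 50 (55 with dropout) per arm for the primary outcome, with the error rates given as "assuming a two-sided type I error protection of 0.05 and a power of 0.80". Catheter-days needed per arm = (1.96 + 0.842)² × (0.01218 + 0.008526) / (0.01218 − 0.008526)² ≈ 12,170, or about 243 days per patient with 50 per arm. The stated 50 is therefore not reproduced. That is a separate problem, but it explains why so few isolates are expected.

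**Step 1: effect of selection on the resistant share.** Let *f* be the resistant share in the control arm.

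- *The whole 30% reduction falls on susceptible infections.* The share in the impregnated arm is *f*/0.7, so 30, 40, 50 and 60% become 43, 57, 71 and 86%. At *f* = 50% the resistant-CLABSI rate is 12.18 × 0.5 = 6.09 per 1000 catheter-days in both arms (ratio 1.0), while the planned comparison shows 50% vs 71%.
- *Both types are reduced equally.* The share stays at 50% vs 50%, while the resistant-CLABSI rate falls from 6.09 to 8.526 × 0.5 = 4.26 (ratio 0.70).

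**Step 2: expected CLABSIs** = 55 × days × rate / 1000.

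| Days per patient | Control | Impregnated | Total |
|---|---|---|---|
| 5 | 3.3 | 2.3 | 5.7 |
| 7 | 4.7 | 3.3 | 8.0 |
| 10 | 6.7 | 4.7 | 11.4 |
| 14 | 9.4 | 6.6 | 15.9 |

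**Step 3: exact Fisher power** (two-sided, p ≤ 0.05), summing binomial probabilities over all significant tables, for a true 50% vs 90% resistant:

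| Isolates (control vs impregnated) | Power |
|---|---|
| 3 vs 2 | 0% (smallest possible p is 0.10) |
| 4 vs 3 | 5% |
| 5 vs 4 | 13% |
| 6 vs 4 | 8% |
| 7 vs 5 | 14% |
| 9 vs 7 | 28% |

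Power does not rise smoothly, because so few tables are possible at these counts. Averaging over Poisson counts with 55 per arm:

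| True resistant shares | 5 days | 7 days | 10 days | 14 days |
|---|---|---|---|---|
| 50% vs 71% | 0.9% | 2.1% | 4.0% | 6.8% |
| 30% vs 60% | 1.8% | 4.2% | 8.1% | 13.5% |
| 20% vs 80% | 7.6% | 18% | 35% | 54% |

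For 80% power, about 42 CLABSIs per arm are needed for 30% vs 60%, and 81 per arm for 50% vs 71%.

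**Step 4: precision of a resistant-CLABSI rate ratio.** With a true ratio of 1 and *f* = 50%, expected resistant events per arm are *e* = 55 × days × 6.09 / 1000, and the approximate 95% limits are exp(±1.96 × √(2/*e*)).

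- 7 days: *e* = 2.34, interval 0.16 to 6.1
- 10 days: *e* = 3.35, interval 0.22 to 4.5
- 14 days: *e* = 4.69, interval 0.28 to 3.6

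**The case against.** **Resistance can be observed only in an isolate.** This is true, and it justifies describing isolates among infected patients. It does not justify comparing arms on them: a resistant CLABSI can be counted in every randomised patient, with uninfected patients contributing catheter-days and no event.

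**The bias is not certain.** This stands. A reader might infer that the planned analysis will make the impregnated catheter appear to raise resistance. The documents do not say which infections the catheter prevents, and equal prevention leaves the share unchanged. A reader might also picture 50% against 100% resistant; with the planned 30% reduction, a 50% control share can reach at most 71% through loss of susceptible infections alone. At these counts such a shift would rarely be significant, so the likelier harm is a misread percentage, not a false-positive test.

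**A test on resistance is inferred.** This also stands in part. Section 3.9 assigns none, and section 3.7.1.2 speaks of profiles. But section 2 says the arms will be compared, and the general rule is the only method offered.

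**A rate answers a different question.** Correct. A catheter that prevents every kind of CLABSI equally would lower the resistant-CLABSI rate without altering the features of the bacteria that remain. The rate should therefore sit beside the isolate description and not replace question 4.

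**The rate is imprecise too.** Step 4 confirms it. The rate removes the selection problem, not the shortage of events.

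**Conclusion.** The concern holds in a conditional form. As written, the resistance comparison conditions on a post-randomisation event that the catheter is meant to change, so a difference in resistant share cannot be attributed to the catheter. The possible distortion is 50% vs 71% if the whole planned reduction falls on susceptible infections, and nil if both types are prevented equally.

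The comparison also carries little information: about 6 to 16 CLABSIs in total, and 0% to about 28% power for 50% vs 90%. It would be too strong to say that power is negligible for every contrast, since 20% vs 80% at 14 days reaches 54%. For moderate differences it is low at every catheter time considered.

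These figures rest on the assumed catheter time, resistant shares and one isolate per CLABSI. This is a secondary outcome and does not affect the primary conclusion, but it is one of four research questions and should be corrected.

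**What to change.** In sections 3.7.1.2(iii) and 3.9:

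1. Add as the between-arm measure the rate of CLABSI caused by a resistant organism per 1000 catheter-days, in the same randomised population and catheter-days as the primary outcome, with an exact confidence interval for the rate ratio.
2. Define a resistant organism in advance, for example by drug class or multidrug resistance.
3. Keep species, phenotypes and resistance genes by arm as a descriptive listing of counts without p-values, and state that differences in resistant share among isolates are not a randomised comparison.

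**Cost.** Mostly wording: section 3.7.2 already collects antibiograms, and the primary outcome in section 3.7.1.1 already needs catheter-days. The isolate-level test is given up, and the rate ratio will be imprecise (step 4). One point goes beyond wording. Section 3.4 excludes patients for events after insertion (under 48 hours of catheter time, poor bundle compliance, more than one CVC or other central access). Including all randomised patients means keeping their outcomes and catheter-days, which the protocol does not now provide for.
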